Subjects in the SELECTION-LTE study who are in clinical remission with 200 mg filgotinib q.d. for at least 2 consecutive quarterly visits, will be provided the option to roll-over to the present study at any scheduled visit of the SELECTION-LTE study or at a separate visit.

Subjects will be requested to attend the site for at least 2 screening visits. Depending on the results of FCP (if applicable) and ES at screening, the subject will either be a screening failure (FCP >250 µg/g or ES >1) in the present study and will remain in SELECTION-LTE, or the subject will be eligible (FCP ≤250 µg/g and ES ≤1) and will need to perform the End of Treatment (EoT) assessments in SELECTION-LTE before being randomized to the present study. Subjects who fail screening in the present study may be re-screened once. Re-screening may only be conducted after approval from the sponsor's medical lead (see Section 8.1.3).

Further details on the timing of screening and Day 1 assessments are provided in Section 8.1.

Flare

When a subject experiences an increase in clinical symptoms, a stool sample will be obtained for culture for pathogenic bacteria, ova and parasite evaluation, and *Clostridium difficile* toxin assay.

An endoscopy will be performed in subjects who experience during treatment an increase in clinical symptoms defined as:

- an increase in rectal bleeding subscore by at least 1 point, AND an increase in stool frequency subscore by at least 2 points, AND a *Clostridium difficile* infection is excluded.

An ES-confirmed UC flare is defined as:

- an increase in rectal bleeding subscore by at least 1 point AND an increase in stool frequency subscore by at least 2 points AND an increase in endoscopic subscore by at least 1 point.

Subjects who experience an ES-confirmed UC flare during treatment will be “re-escalated” (see [Definition of Terms](#)) to open-label 200 mg filgotinib q.d. for at least 12 weeks, while maintaining the blind for the treatment at randomization, and should follow the Schedule of Activities after re-escalation ([Section 8.9.2](#)). An ES-confirmed UC flare should be reported as an adverse event (AE), as explained in [Section 8.4.1](#).

Re-escalation

Subjects should follow the Schedule of Activities after re-escalation ([Section 8.9.2](#)).

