- In case of further worsening of symptoms after Week 2 following re-escalation and/or no improvement in pMCS is detected at Week 4, addition of corticosteroid treatment (i.e. orally- and/or rectally-administered corticosteroids) can be considered with a maximum oral dose of 30 mg q.d. prednisone equivalent.
- If the subject does not respond to re-escalation therapy within a timeframe of maximum 12 weeks, the subject will be permanently discontinued from the treatment and invited to remain in the study up to Week 48 (see [Section 5.4.1.1](#)).
- If subject improvement is sufficient in the opinion of the investigator, the subject will restart the regular Schedule of Activities ([Section 8.9.1](#)), starting from the next 12-weekly visit assessments. The subject may continue on open-label 200 mg filgotinib q.d. until the end of the study. Corticosteroid treatment should be tapered off at the discretion of the investigator.

In case symptoms are worsening again after 12 weeks of re-escalation, the disease worsening criteria must be applied, as explained in [Section 5.4.1.3](#).

Study duration

Each subject will be in the study for a minimum of approximately 56 weeks (28 days screening period + 48 weeks of treatment + 4 weeks follow-up) in countries where filgotinib will become commercially available, and for a maximum duration of 216 weeks (approximately 4 years) in case filgotinib will not become commercially available. In case of re-escalation, the subject will remain in the study at least until the next regular scheduled visit after the 12 weeks post re-escalation visit, or until the end of the study in that country, whichever is longer.

In countries where filgotinib becomes commercially available, the study will be terminated for the subjects who have already completed at least 48 weeks of treatment. Subjects will then be requested to attend the EoT visit as soon as possible. For the subjects who have not yet completed

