^f Blood sample for QuantiFERON® test, if applicable, at S1 needs to be taken after signing ICF, preferably 4 weeks before Day 1 to obtain the TB assessment result before randomization. An indeterminate result should be repeated once and the second result (if positive or negative) will be accepted. Subjects who had 2 sequential indeterminate QuantiFERON® tests or a positive QuantiFERON® test during any of the visits of the SELECTION-LTE but do not have active or latent TB at the time of screening, as

EVENT	SCREENING PERIOD		TREATMENT PERIOD						FOLLOW-UP PERIOD	
	S1 ^a	S2	Day 1 ^b	W4	W12 and then every 12 weeks	W24 and then every 24 weeks	W48 ^c and then every 48 weeks	ED	EoT ^d	4 weeks after last IP dose (EoS)
Study Day (D)/ Week (W)				± 3 days	± 7 days	± 7 days	± 7 days			± 3 days
	D-28 to D-1									
Inclusion/exclusion criteria	✓		Prerandomization							
Demographics	✓									
Medical history	✓									
Pregnancy test	✓ ^j			✓ ^j	✓ ^j			✓ ^j	✓ ^j	✓ ^j
FSH test ^k	✓									
Physical examination (symptom-directed)		✓ ^l		✓	✓			✓	✓	✓
Vital signs		✓ ^l		✓	✓			✓	✓	✓
Height	✓									
Weight	✓ ^l			✓	✓			✓	✓	✓

verified by the investigator, or had latent TB and underwent adequate treatment and continued in the SELECTION-LTE, are not required to have a screening QuantiFERON® test. In this case, the subject must be screened for signs and symptoms of TB reactivation.

^g Sigmoidoscopy during screening, at Week 48 and every 48 weeks thereafter, and ED (if applicable), in fasting condition, as per local guidance. In case of a suspected UC flare, an additional sigmoidoscopy is needed. Two biopsies should be collected during every sigmoidoscopy performed during the study.

^h Bowel preparation for screening sigmoidoscopy can only start after signing ICF.

ⁱ Subjects who discontinue the study prior to Week 48 require a sigmoidoscopy at the ED visit.

^j WOCBP only. Serum pregnancy test during screening; urine dipstick pregnancy test at the Week 4 visit, thereafter at the site every 12 weeks, and in-between every 4 weeks at home (±3 days). If a urine test cannot be confirmed as negative (e.g. an ambiguous result), a serum pregnancy test is required to confirm.

^k For postmenopausal women only.

^l Could be taken from SELECTION-LTE. In case assessments listed at S2 are conducted as part of the EoT visit in SELECTION-LTE, the assessments do not need to be repeated and assessment results may be used.

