8.9.2. Schedule of Activities After Re-escalation

Event	TREATMENT PERIOD					After Week 12: Continue with the regular Schedule of Activities, starting with assessments of the next 12-weekly visit until end of the study
	baseline	W2 ^a	W4	W8	W12	
Study Day (D)/ Week (W)		± 3 days	± 3 days	± 7 days	± 7 days	
Physical examination (symptom-directed)	✓		✓	✓	✓	
Vital signs	✓		✓	✓	✓	
Weight	✓		✓	✓	✓	
Hematology	✓		✓	✓	✓	
Chemistry	✓		✓	✓	✓	
Urine pregnancy test ^b	✓		✓	✓	✓	
CRP	✓		✓	✓	✓	
e-Diary instruction & review	✓	✓	✓	✓	✓	

^a Phone contact^b Only for women of childbearing potential

Event	TREATMENT PERIOD					
	baseline	W2 ^a	W4	W8	W12	
Study Day (D)/ Week (W)		± 3 days	± 3 days	± 7 days	± 7 days	After Week 12:
Dispense IP	✓		✓	✓	✓	12-weekly visit until end of the study
Concomitant medications	✓	✓	✓	✓	✓	
Dose IP	q.d. starting from dispensing of unblinded re-escalated IP ^c					
AE assessments	throughout the study					

AE: adverse event; CRP: C-reactive protein; [REDACTED] q.d.: once daily.

^c If the subject has already taken IP on the re-escalation baseline day, the first adjusted dose should be taken on Day 2 of re-escalation.

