9.3.2. Interim Analysis

An interim analysis is planned for this clinical study.

The data collected from this study will be analyzed at 2 time points. An unblinded interim analysis of the clinical study data will be performed by the sponsor on cleaned and locked data, after the last subject completed their Week 48 postbaseline visit or has completed their Week 12 post re-escalation visit (if baseline of re-escalation is within the first 48 weeks of the study), or after the last follow-up of subjects discontinuing prior to Week 48, whichever comes last. This analysis will be the primary analysis. The analyses will be conducted on efficacy data up to Week 48 and safety data up to the data cut-off date, to be able to evaluate the primary, secondary, and exploratory efficacy endpoints, and safety. The subjects and the clinical study team will be unblinded at the time of the Week 48 analysis (for details, refer to Section 6.4.2).

The final analysis will be performed after the global end of the study (i.e. date of the last visit for the last subject in the last country) and the database is cleaned and locked. At the final analysis, all available efficacy and safety data will be summarized using descriptive statistics.

Details on the interim analysis and the final analysis will be further described in the SAP.

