9.3.4.1.2. Secondary Efficacy Estimand

The secondary estimand for the primary endpoint targets to estimate the effect of decreasing the filgotinib dose from 200 mg q.d. to 100 mg q.d. versus remaining on 200 mg q.d. on corticosteroid-free mMCS remission at Week 48, regardless of flare, permanent treatment discontinuation, or temporary treatment interruptions, in subjects who are in stable clinical remission at study entry. The effect size will be estimated using the Mantel-Hanszel method and expressed as a difference in proportions.

The secondary estimand for the primary endpoint is described according to the following attributes:

Primary Endpoint	Secondary Estimand
Treatment	Filgotinib 100 mg q.d. and filgotinib 200 mg q.d. as randomized.
Population	Subjects who are in stable clinical remission on filgotinib 200 mg q.d. defined through the appropriate inclusion / exclusion criteria.
Variable	Binary corticosteroid-free mMCS remission at Week 48.
Intercurrent events including strategy for addressing them	
– ES-confirmed UC flare: Data collected for subjects randomized to the filgotinib 100 mg q.d. or 200 mg q.d. group for any visit after the re-escalation visit will be included in the analyses (Treatment policy strategy).– Permanent treatment discontinuation: Data collected for subjects who discontinue treatment prior to Week 48 will be included in the analyses (Treatment policy strategy).– Any temporary treatment interruption: Data collected for subjects who temporarily interrupt treatment will be included as reported in the analysis (Treatment policy strategy).
Population-level summary	The treatment difference in the percentage of subjects meeting corticosteroid-free mMCS remission criteria between the filgotinib 100 mg q.d. group and 200 mg q.d. group.
Estimator	The adjusted proportion difference (filgotinib 200 mg – filgotinib 100 mg) with corresponding 95% CI as calculated by a stratified Mantel-Haenszel test (stratification factor: baseline ES [0 or 1]).

In both the primary and secondary estimands for the primary endpoint, any subjects with missing data at Week 48 will primarily be considered as nonresponders. Additional sensitivity analyses may be defined in the SAP.

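### Subjects re-escalated between about Week 36 and Week 48 who stay on treatment have no clearly scheduled Week 48 mMCS, so the treatment-policy estimand of the primary endpoint would score them as failures unmeasured

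*Protocol*

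**What the plan says.** **Schedule after a flare.** Protocol section 5.1 says that subjects with an ES-confirmed flare move to open-label treatment "and should follow the Schedule of Activities after re-escalation". That schedule (section 8.9.2) has a baseline and Weeks 2, 4, 8 and 12. Its visible rows include CRP and e-Diary review, but not sigmoidoscopy, mMCS or FCP. After its Week 12 the instruction is: "Continue with the regular Schedule of Activities, starting with assessments of the next 12-weekly visit until end of the study". Section 5.1 agrees: if improvement is sufficient, "the subject will restart the regular Schedule of Activities", from the next 12-weekly visit. The minimum stay is tied to the same point: "the subject will remain in the study at least until the next regular scheduled visit after the 12 weeks post re-escalation visit", or the end of the study in that country if later.

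**When remission is measured.** Footnote g of section 8.9.1 reads: "Sigmoidoscopy during screening, at Week 48 and every 48 weeks thereafter, and ED (if applicable". It adds a further sigmoidoscopy for a suspected flare. The mMCS footnote gives the same scheduled pattern: screening, every 48 weeks, and early discontinuation.

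**What the estimand needs.** The secondary estimand of the primary endpoint (section 9.3.4.1.2) is corticosteroid-free mMCS remission at Week 48 whether or not a flare occurred. Data from re-escalated subjects "for any visit after the re-escalation visit will be included in the analyses (Treatment policy strategy". For both estimands, "any subjects with missing data at Week 48 will primarily be considered as nonresponders".

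**Subjects who stop treatment.** Section 5.4.1.1 invites anyone who stops study treatment to keep the scheduled visits up to Week 48. No matching sentence covers a re-escalated subject who continues treatment.

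**SAP.** Section 2.4.2 repeats the re-escalation schedule unchanged.

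**The concern.** The secondary estimand asks whether de-escalation, with a return to 200 mg after flare, costs remission at Week 48. To answer that, remission must be measured at Week 48 in subjects who flared. For late flares the schedule appears to move the subject past that visit, and the missing-data rule then supplies the answer. For those subjects the treatment-policy estimand turns into the composite primary estimand, which already counts flare as failure.

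The gap is also selective. A late-flare subject who stops treatment before Week 48 is invited to the Week 48 visit and can be measured. One who improves and continues has no such instruction. The subjects most likely to have regained remission are therefore the ones scored as failures without being seen. If flares are more frequent on 100 mg, the error falls mainly on that arm and makes de-escalation look worse than it is.

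**Working it through.** **1. Yardstick: the plan's own precision.** Section 9.1 states half-widths between 11% and 22.5% for 40 subjects per group, using continuity-corrected Newcombe limits. Recomputing (upper minus lower limit, divided by 2): 20/40 versus 20/40 gives 22.54 points, the maximum over all pairs of counts; 40/40 versus 40/40 gives 10.91. Both stated figures are reproduced.

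**2. Calendar.** For re-escalation at Week T, the re-escalation Week 12 visit falls at T + 12. The next regular visit is the next multiple of 12, and the next scheduled mMCS is the next multiple of 48 from there.

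| T | T + 12 | Next regular visit | Next scheduled mMCS |
|---|---|---|---|
| 30 | 42 | 48 | 48 |
| 35 | 47 | 48 | 48 |
| 36 | 48 | 48 or 60, depending on how next is read | 48 or 96 |
| 37 | 49 | 60 | 96 |
| 40 | 52 | 60 | 96 |
| 47 | 59 | 60 | 96 |

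The gap is T after 36 and before 48.

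**3. Visit windows.** Week 48 and re-escalation Week 12 each have a window of ±7 days. The two can share a day if T + 12 − 1 ≤ 48 + 1, that is, T ≤ 38. A flare sigmoidoscopy from Week 47 on can fall inside the Week 48 window. If sites used both overlaps, the gap would shrink from 12 weeks to about 47 − 38 = 9 weeks. With flares spread evenly over 48 weeks, the late share is then 9/48 = 19% rather than 12/48 = 25%, so 25% is an upper figure under that assumption.

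**4. Size of the bias.** The documents give no flare rates, timing of flares or chance of regaining remission; all three are assumed here. Let s be the share of flares that come late, r the chance that a late-flare subject would be in corticosteroid-free remission at Week 48 if measured, and f100 and f200 the flare rates by Week 48. If every late flare goes unmeasured:

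Overstatement of (200 mg − 100 mg) = s × r × (f100 − f200)

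- Low: 0.15 × 0.20 × (20 − 10) = 0.3 points.
- Central: 0.25 × 0.40 × (30 − 10) = 2.0 points.
- High: 0.25 × 0.60 × (30 − 10) = 3.0 points.
- Equal flare rates: 0 points.

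Pushing every assumption further (s = 0.35, r = 0.60, 40% versus 10%) gives 0.35 × 0.60 × 30 = 6.3 points, but that needs flares concentrated late as well as a large gap between arms.

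**5. Central case in full.** Take 85% remission without flare and 40% after any flare, if measured.

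- Measured, 200 mg: 0.90 × 85 + 0.10 × 40 = 80.5%. Measured, 100 mg: 0.70 × 85 + 0.30 × 40 = 71.5%. Difference 9.0 points.
- Late quarter of flares scored as failures, 200 mg: 76.5 + 0.10 × 0.75 × 40 = 79.5%. The same for 100 mg: 59.5 + 0.30 × 0.75 × 40 = 68.5%. Difference 11.0 points.

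Late flares expected with 40 per arm: 40 × 0.10 × 0.25 = 1 on 200 mg and 40 × 0.30 × 0.25 = 3 on 100 mg.

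**The case against.** **Footnote g has no exception for re-escalated subjects, and nothing says outright that Week 48 is omitted.** This is fair. The skip follows from combining two schedules, and a careful site might still bring the subject in. But the footnote belongs to the schedule these subjects have left, and section 5.4.1.1 shows that the protocol writes out Week 48 attendance where it intends it. What stands is a conflict between passages rather than an explicit omission.

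**Rows of 8.9.2 may be redacted.** This is possible. Section 5.1 relies on a pMCS at re-escalation Week 4, yet no pMCS or PGA row is printed. SAP section 6.3.1.3 would list mMCS at re-escalation visits if applicable, though that may mean only the flare endoscopy. Against this, the sigmoidoscopy and mMCS rows are visible in 8.9.1 and their footnotes name no re-escalation visit. IBDQ has no visible row in either schedule, so a loss of Week 48 IBDQ cannot be inferred.

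**Some late flares are measured.** This is correct. Subjects who stop treatment can attend Week 48, and those who leave the study before Week 48 have an early-discontinuation sigmoidoscopy. A reader might infer that no Week 48 data exist for any late flare; the documents do not support that.

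**Few would have regained remission.** Under even spread, a late flare comes on average 6 weeks before Week 48. Anyone given corticosteroids after re-escalation fails the 12-week corticosteroid-free condition and is a true nonresponder. High regain rates, such as 80%, are therefore implausible.

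**The analysis trigger.** Section 9.3.2 waits until "after the last subject completed their Week 48 postbaseline visit or has completed their Week 12 post re-escalation visit". A reader might take these as alternatives, so that Week 48 could be bypassed. The sentence goes on to require the latest of the listed events, as does section 6.4.2, so the trigger needs no change.

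**Conclusion.** The point holds for the protocol as written and is modest in size. For subjects re-escalated after about Week 36 and before Week 48 who stay on treatment, sections 5.1 and 8.9.2 conflict with footnote g and with section 9.3.4.1.2. Following 8.9.2 literally moves the secondary estimand toward the composite primary estimand for late flares. The 200 mg minus 100 mg difference is then overstated by roughly 0.3 to 3 points if 100 mg flares more, and by zero if flare rates are equal. These figures rest on assumed flare rates, timing and regain, and treat every late flare as unmeasured, which errs on the high side. They are small beside a 22.5-point half-width in a study without hypothesis testing, and section 9.3.4.1.2 allows sensitivity analyses of the missing-data rule.

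The primary estimand is unaffected, because it scores these flares as nonresponse by design. A Week 48 FCP value would also be missed on the literal reading, but section 9.3.4.2.1 handles that in a mixed model under missing at random and does not score it as failure.

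A reader might infer that the reported results are biased. They are not: the SAP records 22 randomized subjects (section 2.4.3) and termination before anyone reached Week 48, with the primary endpoint only listed (section 6.1). It does not impute data missing because the study stopped (section 4.4.1.2). The defect lies in the planned estimand and matters for reuse of the design.

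**What to change.** Reconcile sections 5.1 and 8.9.2 with footnote g of section 8.9.1 by one sentence on assessments: the Week 48 visit, counted from randomization, is performed for every subject still in the study, including those within 12 weeks of re-escalation, with its planned sigmoidoscopy, mMCS and FCP. It may be combined with a re-escalation visit that falls in the window, and a flare sigmoidoscopy inside the Week 48 window may serve. Treatment after re-escalation is not touched.

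The cost is one sentence and a column note. No new type of procedure is added, since footnote g already plans the Week 48 sigmoidoscopy without exception. The downside is that a late-flare subject has that sigmoidoscopy within 12 weeks of the flare sigmoidoscopy. For the terminated study nothing needs to be reanalysed.

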9. STATISTICAL METHODS

All statistical methods shall be detailed in a statistical analysis plan (SAP). The SAP will be finalized prior to the interim analysis (see Section 9.3.2) and unblinding. All relevant data collected in this clinical study will be documented using summary tables, figures, and subject data listings.

Any deviations from the CSP are to be justified in the SAP.

9.1. Determination of Sample Size

The primary objective is to estimate the difference in remission rates at Week 48 between 200 mg filgotinib q.d. and 100 mg filgotinib q.d. No formal hypothesis testing will be conducted.

The sample size is determined based on the desired level of precision (half width of the 95% CI) of the estimated treatment difference between 200 mg filgotinib q.d. and 100 mg filgotinib q.d. in the percentage of subjects meeting corticosteroid-free¹ mMCS remission criteria at Week 48. The level of precision determines the range in which the treatment difference is estimated to be. This range is expressed in percentage points.

The highest variability in the estimation of the treatment effect (i.e. CI with the lowest precision, or largest width) is observed when the remission rate is 50%. Figure 2 shows the worst-case precision for a range of observed treatment differences when the remission rate is 50% in at least one treatment group for a fixed set of possible sample sizes ranging from 30 subjects to 70 subjects per group (assuming 2 groups of equal size). Continuity-corrected Newcombe confidence limits were used to calculate the precision. The precision is better if the actual observed remission rates differ from 50%. A sample size of 40 subjects per group will guarantee a worst-case precision of maximum 22.5%.

¹ Free of corticosteroids for at least 12 weeks.

[figure not shown]

Figure 2: Worst-case Precision for a Range of Sample Sizes Using Newcombe Continuity-corrected CIs With 50% Remission Rate in at Least 1 Group

Figure 3 shows the precision achieved for a range of potential treatment differences for a sample size of 80 subjects. With 40 subjects per group, the estimated half width of the 95% CI for the treatment difference between filgotinib 200 mg q.d. and 100 mg q.d. will lie within 11% and 22.5%.

[figure not shown]

Figure 3: Precision for a Sample Size of 40 Subjects per Group Using Newcombe Continuity-corrected CIs

9.2. Population for Analyses

9.2.1. All Screened Subjects

All subjects who signed and dated an ICF.

